8.1.3. Analyses

A modified intention-to-treat approach to all analyses will be used, including all study participants randomized to therapy and have the outcome of interest measured including all

follow-up time until the study participants complete the study or early study termination regardless of whether the intervention was stopped due to an adverse event.

Primary analysis. We will compare the risk of having any adverse birth outcome between the study arms using the Chi-Square or Fisher's exact test. We will explore for any differences of potential confounders between the treatment arms and if necessary adjust our analysis using multivariate logistic regression. We will also perform sub-group analyses comparing the risks of having individual adverse birth outcome (LBW, preterm delivery, SGA) between the study arms using the Chi-Square or Fisher's exact test.

Secondary analyses. We will compare the prevalence of different definitions of placental malaria (placental parasitemia by microscopy, placental malaria by LAMP, placental malaria by histopathology) using the Chi-Square or Fisher's exact test. We will compare the incidence of maternal malaria and adverse events using Poisson or negative binomial regression models. The Poisson models will include the logarithm of the follow-up time as an offset. We will translate the fitted coefficients and their confidence bounds into percentage effects with the formula 100*[exp(coefficient)-1]. This approach is closely related to exponential survival models for analyzing events per follow-up time, but is better able to adjust for violated assumptions. Testing for overdispersion in the Poisson regression can detect violations of these assumptions, and variances can be adjusted accordingly to produce valid p-values and confidence interval. If significant deviations from required distributions in study data are detected, we will employ negative-binomial or zero-inflated negative-binomial models to account for the observed pattern of data. We will compare the prevalence of maternal anemia and asymptomatic parasitemia using generalized estimating equations with adjustments for repeated measures in the same study participant. If necessary, multivariate analyses will be performed to adjust for potential confounders and effect modifiers.

8.2. Hypothesis 2

We will test the hypothesis that infants born to mothers randomized to IPTp with monthly DP will have a lower incidence of malaria in the 1st year of life compared to infants born to mothers randomized to IPTp with monthly SP. Secondary outcomes will include the incidence of complicated malaria, hospitalizations, infant mortality rate, and the prevalence of asymptomatic parasitemia and anemia.

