4.3. Initial Screening

We will recruit pregnant women presenting for routine care at the Masafu General Hospital antenatal clinic, at local health centers within Busia District, or referred by the Uganda government voluntary health teams. Pregnant women will be approached about participating in the study and will be provided an information sheet about the requirements of the study (Appendix A). If women are initially agreeable to screening for participation in the study and are ≤ 20 weeks gestation by LMP, 16 years of age or older, and not known to be HIV infected, they will either be escorted to the study clinic or made an appointment to return at a later date. At our study clinic study physicians will assess for initial eligibility criteria through conversation with the woman (confirming the age of the woman, location of residence, agreement to come to the study clinic for any febrile episode or other illness and avoid medications given outside the study protocol, plan to deliver in the hospital, no history of serious adverse event to SP or DP, no active medical problems requiring inpatient evaluation at the time of screening, no intention of moving outside the study district, no chronic medical condition requiring frequent medical attention, and no prior SP preventive therapy or any other antimalarial therapy during

this pregnancy). Women who pass initial screening based on conversation with study physicians will undergo the following additional screening procedures: 1) rapid HIV testing to confirm HIV negative status, 2) ultrasound dating to confirm intrauterine pregnancy and gestational age of 12-20 weeks in conjunction with LMP (Appendix B), and 3) a pelvic examination to exclude early or active labor if clinically indicated. Women who are not eligible for the study will be referred back to their local antenatal clinic.

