Women will be enrolled in study on the same day that they provide informed consent for participation in the research study. On the day of enrollment, women will undergo a standardized history and physical examination, and have blood collected by venipuncture (15 cc's) for filter paper sample (for future molecular studies), routine baseline laboratory testing and storage. Routine baseline laboratory testing will consist of a thick blood smear for malaria parasites (will be read later by laboratory technicians not involved in study participants care and will not used for clinical care), RDT testing including a standard RDT using a PTS reader and an experimental RDT (results will not be used for clinical care), qPCR for malaria parasites, CBC and ALT measurement. Women who have history of fever in the previous 24 hours or a temperature \geq 38.0°C (tympanic) will have a thick blood smear read urgently in the study clinic. Women with history of fever in the previous 24 hours or a temperature \geq 38.0°C (tympanic) and a positive blood smear will be diagnosed with malaria and treated as described in section 6.2. At the end of the enrolment visit all study participants will be given a long lasting insecticide treated bed net (ITN) and a household survey appointment will be scheduled within 2 weeks to collect household-level information on the use of bednets, house members, household characteristics, and GPS coordinates (Appendix C).

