5. STUDY TREATMENT

5.1. Treatment Group Assignments

There will be 2 treatment arms for the woman during pregnancy; monthly SP or monthly DP. We will use a 1:1 randomization scheme targeting 391 pregnant women in each treatment arm. A randomization list will be computer generated by a member of the project who will not be directly involved in the conduct of the study. The randomization list will include consecutive treatment numbers with corresponding random treatment assignments. Randomized codes will correspond to the 2 treatment arms using permuted variable sized blocks of 4 and 8. Sealed copies of the original randomization list and documentation of the procedure used to generate the lists will be stored in the project administrative offices in San Francisco and Kampala. Prior to the onset of the study, a set of sequentially numbered, opaque, sealed envelopes will be prepared. Each envelope will be marked on the outside with the treatment allocation number. The inside of the envelope will contain a piece of paper with the treatment allocation number and treatment group assignment along with a piece of carbon paper.

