8.1.1. Primary Outcome

The primary outcome will be the risk of having an adverse birth outcome defined as the occurrence of any of the following:

- 4) Low birth weight (< 2500 gm)
- 5) Preterm delivery (< 37 weeks gestational age)
- 6) Small for gestational age (< 10th percentile relative to an external growth reference)⁷³

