8.2.3. Analyses

A modified intention-to-treat approach to all analyses will be used, including all live infants born and including all follow-up time until the study participants reach 12 months of age or early study termination regardless of whether the infant's mother received her assigned IPTp regimen.

Primary analysis. We will compare the incidence of malaria using Poisson or negative binomial regression models as described in section 8.1.3. If necessary, multivariate analyses will be performed to adjust for potential confounders and effect modifiers.

Secondary analyses. We will compare the incidence of complicated malaria and hospitalizations using Poisson or negative binomial regression models as described in section 8.1.3. We will compare the prevalence of anemia and asymptomatic parasitemia using generalized estimating equations with adjustments for repeated measures in the same study participant. If necessary, multivariate analyses will be performed to adjust for potential confounders and effect modifiers.

8.3. Hypothesis 3

We will test the hypotheses that a metabolic dating algorithm developed in a western setting can also be used for gestational dating in Uganda. We will also test the hypothesis that metabolic markers – especially those related to glucose metabolism can be used to identify newborns at more or less risk for death and serious morbidities.

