8.4. Sample size and power

The number of pregnant women enrolled and the number of study participants reaching the various endpoints will determine the samples sizes for each of the primary outcomes of our study aims. The primary determinant of our target sample size was based on testing hypotheses 1. Based on our previous studies, we estimate that 95% of pregnant women enrolled will reach the primary study endpoint and we will lose 5% of follow-up time per year in the infants. The study will be powered to detect a significant difference in the risk of our composite adverse birth outcome between the 2 study arms. Considering pregnancies resulting in either low birth weight (< 2500 gm), small for gestational age, or premature delivery (< 37 weeks) in our previous study, the risk was 21.4% in the monthly DP arm compared to 30.4% in the 3 dose SP arm. Assuming the same risks, we would need to enroll 782 women (assuming 5% loss to follow-up during pregnancy) to have 80% power (2-side alpha = 0.05) to detect a 30% or greater reduction in the relative risk of our composite birth outcome. For hypothesis 2, we will have 80% power (2-side alpha = 0.05) to detect an 18-23% relative difference in the incidence of malaria between 0-12 months of age among children born to mothers randomized to the 2 IPTp arms assuming an incidence of malaria ranging from 3-5 episodes PPY among children born to mothers randomized to receive IPTp with monthly SP. Hypothesis 3 relies on the collected study data and samples to validate existing gestational dating, survival, and morbidity algorithms and as such, no limitations in statistical power are anticipated.

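### The primary comparison is adjusted only if the arms happen to differ at enrolment; a fixed covariate list would be a low-cost efficiency improvement

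*Combined protocol and SAP*

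**What the plan says.** Section 8.1.3 compares the composite between arms with a chi-square or Fisher's exact test. The next sentence reads: "We will explore for any differences of potential confounders between the treatment arms and if necessary adjust our analysis using multivariate logistic regression". It lists no covariate, no measure or threshold of imbalance, and no rule for which covariates enter once a difference is found. It also does not say whether the adjusted or the unadjusted result would then be primary.

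Section 5.1 describes 1:1 allocation: "Randomized codes will correspond to the 2 treatment arms using permuted variable sized blocks of 4 and 8". No stratification factor is stated.

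The outcome in Section 8.1.1 is a risk: "The primary outcome will be the risk of having an adverse birth outcome". Section 8.4 plans the trial "to detect a 30% or greater reduction in the relative risk of our composite birth outcome".

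Usable baseline data are already in the schedule. Section 4.3 covers "confirming the age of the woman" and "ultrasound dating to confirm intrauterine pregnancy and gestational age of 12-20 weeks in conjunction with LMP". Section 4.4 adds a standardised history and examination and "qPCR for malaria parasites, CBC and ALT measurement". Appendix G includes weight, and height at enrolment.

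Section 8.2.3 uses similar open wording for infant malaria: "If necessary, multivariate analyses will be performed to adjust for potential confounders and effect modifiers".

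**The concern.** With randomised allocation and no stratification, a difference between arms at enrolment is a chance difference. Looking for such differences cannot identify a confounder in the usual sense. It can only show which covariates fell unevenly this time. The statistical reason to adjust in a randomised trial is that prognostic covariates reduce the variance of the treatment comparison, and they do so whether or not they happen to be imbalanced. A rule that waits for imbalance therefore leaves part of that benefit unused.

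Two smaller matters follow. First, because the trigger is undefined, there may be two results on the table with nothing saying which one counts. Second, logistic regression yields a conditional odds ratio, while the outcome and the sample size are stated on the risk scale.

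**Working it through.** **Reproducing the plan's figure.** Inputs from Section 8.4: 30.4% (SP) and 21.4% (DP), 80% power, two-sided 0.05, 5% loss. The pooled two-proportion formula, with mean risk 0.259, is

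n = [1.960·√(2·0.259·0.741) + 0.842·√(0.304·0.696 + 0.214·0.786)]² / 0.090² = 370.8, so 371 per arm.

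Then 742/0.95 = 781.05, so 782. The plan's number is exactly that of an unadjusted comparison.

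**Assumptions that the documents do not supply.** Six covariates (one binary with 25% prevalence, five standard normal); outcome R² of 0, 2, 8 or 16% (AUC 0.50, 0.59, 0.67, 0.75); imbalance judged by a test at p<0.05 or p<0.20.

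**How often a trigger fires.** With six covariates, 1 − 0.95⁶ = 26% at p<0.05 and 1 − 0.80⁶ = 74% at p<0.20.

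**Power (%), 371 per arm, 16,000 simulated trials per scenario** (Monte Carlo SE about 0.3 points; at most 0.24 for paired differences). Here only the imbalanced covariates enter the triggered model.

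| Analysis | R² 0 | R² 2% | R² 8% | R² 16% |
|---|---|---|---|---|
| Unadjusted chi-square | 79.9 | 80.4 | 79.8 | 80.6 |
| Trigger at p<0.05 | 79.7 | 80.2 | 80.3 | 81.0 |
| Trigger at p<0.20 | 79.7 | 80.4 | 80.6 | 81.9 |
| Fixed adjustment, standardised risk ratio | 79.5 | 80.5 | 82.5 | 86.0 |

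The paired change from unadjusted to fixed is -0.4, +0.1, +2.8 and +5.4 points. Smaller runs agree to within their error: one of 5,000 trials gave 80.3 to 82.1 at R² 8% and 80.2 to 85.7 at 16%.

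**Share of the power gain kept, imbalanced covariates only** (unrounded differences).
- p<0.05: 0.52/2.77 = 19% at R² 8%; 0.41/5.42 = 8% at 16%.
- p<0.20: 0.86/2.77 = 31% and 1.28/5.42 = 24%. A further run of 6,000 trials reached 37%.
- These shares are noisy at R² 8%. The 5,000-trial run, with a standard error of about 0.6 points, showed no gain there for the p<0.20 trigger (80.2 against 80.3).
- A separate normal-approximation calculation gives 12% and 34%.

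**Share of the sampling-variance gain kept, same rule.** For threshold a and c = z(1−a/2), the share is a + 2cφ(c).
- a = 0.05: 0.05 + 2·1.960·0.0584 = 0.28.
- a = 0.20: 0.20 + 2·1.282·0.1755 = 0.65.
- Simulations gave 23 to 31% and 59 to 66%.

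**If any one imbalance brings in the whole set.** With six covariates the power share is about 26 to 41% at p<0.05 and 77 to 80% at p<0.20; the variance share reaches 86 to 89% at p<0.20. In the normal approximation five covariates give power shares of 29% and 73%. Eight covariates give 38% and 86%, with a variance share of up to 93%.

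**Error rates and disagreement.** Type I error is 4.1 to 4.9% for the triggers and 4.8 to 5.2% for fixed adjustment. Across the four strengths, unadjusted and triggered results fall on opposite sides of 0.05 in 0.5 to 2.6% of trials (p<0.05 trigger) and 1.4 to 6.2% (p<0.20 trigger).

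**Scale.** RR = 0.214/0.304 = 0.70. Crude OR = (0.214/0.786)/(0.304/0.696) = 0.62. As R² rises the adjusted OR averages 0.62, 0.61, 0.60 and 0.57, while the standardised RR stays at 0.70.

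**Room in the model.** Expected events are 371 × (0.304 + 0.214) = 192, or 192/8 = 24 per term for treatment plus seven covariates.

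**The case against.** The case for leaving the text alone is strong. The chi-square test is valid, reads naturally as primary and is the test the trial was sized on. Restricting the search to potential confounders already suggests variables related to outcome, and no significance test of imbalance is stated. The precision gain rests on assumed prognostic strengths; at the two weakest it is nil or slightly negative. One sentence naming the chi-square test as primary would settle which result counts. All of this stands, and it makes the point an efficiency matter.

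Three stronger readings are tempting and are not supported:
- A reader might infer that the trigger keeps a third or less of any available precision. That is roughly right for power if only imbalanced covariates enter. It fails for sampling variance at p<0.20, and for both measures at p<0.20 if one imbalance brings in the full set, which Section 8.1.3 also permits.
- A reader might infer inflated type I error. A mechanically applied trigger is slightly conservative. A rate of 6.0 to 7.1% (R² 5 to 20%) arises only if the analyst may report whichever test is significant. The wording does not exclude that, but nothing in the documents proposes it.
- A reader might carry the power gain over to Hypothesis 2. No gain was calculated for that count outcome, and covariates that predict birth outcome need not predict infant malaria.

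The objection does not show that waiting for imbalance has any advantage when covariates are prognostic.

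**Conclusion.** The point holds as an optional, low-cost improvement. It is not an error in the primary test. Under Section 8.1.3, chance imbalance rather than prognostic value decides whether the primary comparison is adjusted, and the choice between two results is left open.

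With six assumed covariates and 371 per arm, fixed adjustment is worth about -0.4 power points (no prognostic value), 0 (R² 2%), +2 to +3 (8%) or +5 to +6 (16%). At the two larger strengths the trigger keeps roughly:
- imbalanced covariates only: 10 to 20% of the power gain at p<0.05 and 25 to 37% at p<0.20;
- whole set on any imbalance: 25 to 40% at p<0.05 and 75 to 80% at p<0.20.

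Every version simulated at those two strengths kept less than fixed adjustment. The direction of the result is firm if the covariates are prognostic. Its size is not, because the documents fix none of the inputs beyond the design risks and the sample size.

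**What to change.** Delete the imbalance trigger from Section 8.1.3. Before unblinding, fix a short list of prognostic enrolment covariates already collected: for example gestational age, maternal age, height, weight, haemoglobin and qPCR parasite status, plus gravidity if the enrolment history records it. Adjust for them whatever the imbalance. Report a standardised (marginal) risk ratio and risk difference with 95% CI.

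Fill missing covariates by a simple arm-blind rule, such as the mean over both arms with a missing category for qPCR, so that no woman with an outcome is dropped. If 5% of each of six covariates were missing independently (an assumption), dropping incomplete records would lose 1 − 0.95⁶ = 26% of women. Mean filling at that rate left simulated power at 79.6, 80.5, 82.4 and 85.6% across the four strengths.

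Make this the primary analysis, with the chi-square test supportive. If the sponsor keeps the chi-square test primary, say so and label the fixed adjusted analysis as supportive, accepting that the primary test then gains no power.

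For Hypothesis 2, the open wording in Section 8.2.3 has the same weakness. Any fixed list there should be chosen for infant malaria, for example from the household survey in Appendix C.

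The cost is a change of analysis wording, with no new data and no change to 782. A model replaces a 2×2 table, and about 0.4 power points are lost if the covariates turn out not to be prognostic.

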8.2.1. Primary Outcome

The primary outcome will be the incidence of malaria, defined as the number of incident episodes per time at risk. Incident cases will include all treatments for malaria not proceeded by another treatment in the previous 14 days. Time at risk will begin at birth and will end when study participants reaches 12 months of age or early study termination (if prior to 12 months of age).

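### The incidence analysis, including the Hypothesis 2 primary analysis, may switch to a zero-inflated model on the observed data, and that model's count coefficient need not equal the overall incidence ratio

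*Combined protocol and SAP*

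**What the plan says.** Section 8.2.1 defines the Hypothesis 2 primary outcome as malaria incidence, that is, "the number of incident episodes per time at risk". Section 8.2.3 sets the primary analysis: "We will compare the incidence of malaria using Poisson or negative binomial regression models as described in section 8.1.3". Complicated malaria and hospitalizations are handled the same way.

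The section it points to, 8.1.3, was written for maternal malaria and adverse events. It starts from Poisson or negative binomial regression and states a log follow-up-time offset for the Poisson models only. Fitted coefficients are to be turned into "percentage effects with the formula 100*[exp(coefficient)-1"]. It then allows variances to be adjusted for overdispersion. If the data deviate significantly from the required distribution, "we will employ negative-binomial or zero-inflated negative-binomial models to account for the observed pattern of data". It names no test, threshold, order of models or blinded selection step. It also does not say whether treatment arm would enter the zero part of a zero-inflated model, or which coefficient would be reported.

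**The concern.** A zero-inflated model splits the infants into a structural-zero class, who would have no episodes however long they were followed, and the rest, whose counts follow a negative binomial distribution. The treatment coefficient in the count part compares rates among the rest only. The outcome in 8.2.1 counts episodes over everyone's time at risk.

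If the intervention moves infants into the structural-zero class, that benefit lies outside the count coefficient. Exponentiating the coefficient could then understate, miss or exaggerate the effect on the plan's own outcome. Adjusting variances does not help, because the quantity being estimated has changed. For Hypothesis 2, the meaning of the primary result could therefore depend on an unspecified look at the data.

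**Working it through.** **1. The plan's own figures.** Section 8.4 states "we would need to enroll 782 women (assuming 5% loss to follow-up during pregnancy) to have 80% power (2-side alpha = 0.05"), with event risks given as "the risk was 21.4% in the monthly DP arm compared to 30.4% in the 3 dose SP arm". Section 5.1 adds: "We will use a 1:1 randomization scheme targeting 391 pregnant women in each treatment arm". With the pooled-variance formula, no continuity correction and pbar = 0.259:

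n = [1.96·√(2·0.259·0.741) + 0.8416·√(0.304·0.696 + 0.214·0.786)]² / 0.090² = 370.8, so 371 per arm and 742 evaluable; 742/0.95 = 781.05, so 782.

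This reproduces the plan and does not involve the incidence model.

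**2. What the Hypothesis 2 power statement implies.** Section 8.4 claims 80% power to "detect an 18-23% relative difference in the incidence of malaria between 0-12 months of age" at 3-5 episodes per person-year. I take 371 infants per arm and 0.975 years each (5% of follow-up time lost, on average halfway through), so T = 361.7 person-years per arm.

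- Plain Poisson, SE² = 1/(λT) + 1/(λ·RR·T): detectable reduction 11.7% at 3 per year and 9.1% at 5 per year.
- Variance multiplier needed for the stated range, φ = (ln RR / 2.802)² / SE²: at 3 per year and 23%, 0.00870/0.00212 = 4.1; at 5 per year and 18%, also 4.1.

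The stated range is recovered with variance about four times Poisson. The plan states no dispersion, so this is an inference. It suggests that a departure from plain Poisson is foreseeable.

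**3. Which options change the target.** Poisson, variance-adjusted Poisson and negative binomial models with a log link and offset all estimate the log of the overall rate ratio. They differ in weighting and standard error. For the zero-inflated model, with structural-zero proportions π and count means μ:

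overall ratio = [(1 − π_DP)·μ_DP] / [(1 − π_SP)·μ_SP]

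The count coefficient gives μ_DP/μ_SP, which equals the overall ratio only when π_DP = π_SP. All π values below are assumptions; the documents give none.

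| π_SP | π_DP | Count ratio | Formula reports | True overall change |
|---|---|---|---|---|
| 20% | 20% | 0.80 | −20% | −20% |
| 20% | 30% | 1.00 | 0% | 0.70/0.80 = 0.875, −12.5% |
| 20% | 30% | 0.80 | −20% | 0.875·0.80 = 0.70, −30% |
| 20% | 36% | 1.00 | 0% | 0.64/0.80 = 0.80, −20% |
| 30% | 20% | 0.80 | −20% | (0.80/0.70)·0.80 = 0.914, −8.6% |

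**4. Simulation.** Setup: 371 per arm, one year each, control mean 3 episodes, dispersion 0.5 (assumed), 150 runs per row. Rejection is at the two-sided 5% level. Its Monte Carlo standard error is at most about 4 points (√(0.25/150) = 0.041).

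| Where the effect lies | Zero part | True | Negative binomial (rejects) | Zero-inflated count part (rejects) |
|---|---|---|---|---|
| All in zero part | by arm | −20% | −19.8% (59%) | 0.0% (2%) |
| All in zero part | constant | −20% | −19.7% (58%) | −7.8% (13%) |
| Split | by arm | −20% | −20.5% (71%) | −11.7% (31%) |
| All in count part | by arm | −20% | −19.7% (71%) | −20.0% (79%) |
| All in count part | constant | −20% | −20.8% (78%) | −21.1% (89%) |
| Opposing components | by arm | 0% | +1.2% (3%) | +26.1% (79%) |

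The negative binomial ratio tracks the overall effect throughout. The zero-inflated coefficient does so only when the zero proportions are equal.

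**The case against.** The route into the Hypothesis 2 primary analysis is indirect. Section 8.2.3 names only Poisson or negative binomial models, and the zero-inflated option appears once, as a fallback in 8.1.3. One can read 8.2.3 as excluding it. That reading is possible but not secure, because 8.2.3 adopts the models as 8.1.3 describes them.

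The percentage formula appears before the zero-inflated option. A reader might infer that the plan orders this formula for every model. It does not: it gives no other formula and says nothing about a two-part model.

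A reader might also infer that the zero-inflated coefficient never estimates the incidence ratio, or that any data-driven choice of count model changes the question. Neither is supported. The coefficient agrees when the zero proportions are equal, and the other three options share one target.

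The examples are assumed, and the starkest put the whole effect in the zero part. Many zeros need not trigger the switch. With the negative binomial dispersion implied by the power statement (about 1.2 at 3 per year and 0.7 at 5), the zero probability (1 + kμ)^(−1/k) is already about 28-29% and 12%. This lowers the chance of a switch without excluding it.

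Finally, foreseeable overdispersion does not make Poisson wrong as a starting point, since 8.1.3 already provides for adjusted variances and negative binomial models.

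**Conclusion.** The concern holds in a limited form. The plan permits, on an unspecified data-driven check, a model whose count coefficient need not equal the incidence ratio that 8.2.1 calls for, and it gives no reporting rule to bridge the two. The cross-reference leaves this open for the Hypothesis 2 primary analysis.

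The size depends on how far structural zeros differ between arms, which the documents do not address. Under the assumed values, the reported effect ranged from no effect when the truth was a 20% reduction to a 26% increase when the truth was no difference. With equal zero proportions there was no discrepancy of note. These are illustrations of what could happen, not forecasts.

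A reader might carry the concern over to the trial's main result. The documents do not support that: the birth-outcome comparison uses a chi-square or Fisher's exact test, and 782 follows from it.

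**What to change.** In 8.1.3 and 8.2.3, name one model for all incidence outcomes. Suggested wording: 'Incidence will be compared by negative binomial regression with a log link and log time at risk as offset; the overall incidence rate ratio with its 95% confidence interval is the reported effect.' This also closes the gap that an offset is stated for the Poisson models only. Poisson with adjusted variance would serve the same target if preferred; what matters is fixing one model before the data are seen by arm.

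Delete the zero-inflated model, or restrict it to a sensitivity analysis that reports the marginal (overall) rate ratio and states whether arm enters the zero part.

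The cost is wording only, with no change to sample size or data collection. If the data turn out to be Poisson, I expect at most a small loss of efficiency. I have not computed it, but with equal follow-up and arm as the only covariate both models give the ratio of the arm means, so only the standard error differs.

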6.10.2. Clinical Laboratory Studies

At enrollment and every 8 weeks during follow-up for pregnant women venipuncture blood samples will be collected for routine clinical laboratory studies, including CBC and ALT measurements. In children venipuncture blood samples will be collected for a routine hemoglobin measurement using a portable spectrophotometer (HemoCue Angholm, Sweden) at 12, 28, and 52 weeks of age. Additional venipunctures will be performed, as appropriate, for laboratory testing to evaluate non-malarial medical illnesses at the discretion of study physicians. Results will be made available to study physicians in a timely manner for patient management decision-making. Additional hemoglobin measurements will be performed each time a patient is diagnosed with malaria using a portable spectrophotometer (HemoCue, Angholm, Sweden) and results will be immediately available.

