8.1.2. Secondary Outcomes

Secondary outcomes are summarized in Table 3 below.

Secondary outcome	Definition
Placental malaria by histopathology	Any evidence of placental infection (parasites or
	pigment)
Placental parasitemia	Proportion of placental blood samples positive for
	parasites by microscopy or LAMP
Maternal malaria	Any treatment for malaria during pregnancy
Incidence of adverse events	Adverse events stratified by type, severity score
	and relationship to study drugs
Prevalence of anemia	Proportion of routine hemoglobin measurements
	< 11 g/dL & < 8 g/dL
Prevalence of asymptomatic	Proportion of routine monthly samples positive
parasitemia	for parasites by microscopy and LAMP

Table 3. Secondary outcomes

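### Enrolment haemoglobin is measured in every woman but is not pre-specified as a covariate in the maternal anaemia GEE, which gives up precision on a named secondary outcome

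*Combined protocol and SAP*

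**What the plan says.** Section 4.4 describes blood drawn from all women on the day of enrolment. "Routine baseline laboratory testing will consist of a thick blood smear for malaria parasites", and the same list goes on to "qPCR for malaria parasites, CBC and ALT measurement". Section 6.10.2 repeats the blood count through pregnancy: "At enrollment and every 8 weeks during follow-up for pregnant women venipuncture blood samples will be collected for routine clinical laboratory studies". Appendix G places these draws at enrolment, weeks 20, 28 and 36, and delivery. It drops the week-20 draw for women enrolled at about 18 to 20 weeks. Appendix D starts study drug at week 16.

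Table 3 in section 8.1.2 defines maternal anaemia per sample, as "Proportion of routine hemoglobin measurements" below 11 g/dL and below 8 g/dL. It does not say whether the enrolment sample is one of them.

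The planned analysis in section 8.1.3 is: "We will compare the prevalence of maternal anemia and asymptomatic parasitemia using generalized estimating equations with adjustments for repeated measures". The next sentence allows multivariable adjustment for possible confounders and effect modifiers where this proves necessary. It names no covariate and does not say what would make adjustment necessary.

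**The concern.** Allowing for repeated measures in a GEE handles the correlation among one woman's samples. It does not condition on where she started. Haemoglobin late in pregnancy is expected to depend on haemoglobin at enrolment, so leaving that value out keeps predictable between-woman variation in the error of the treatment comparison.

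The conditional clause does not fill the gap. It is aimed at confounding. In a randomised trial the outcome's own baseline is used for precision, whether or not the arms look unbalanced. As written, the choice would be made after the data are seen, which leaves two possible analyses for one outcome.

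At stake is the precision of a named secondary outcome of Objective 1. The primary birth-outcome test is not affected.

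**Working it through.** **The plan's own figure.** The only stated power for the women is for the composite birth outcome: "the risk was 21.4% in the monthly DP arm compared to 30.4% in the 3 dose SP arm" and "we would need to enroll 782 women (assuming 5% loss to follow-up during pregnancy) to have 80% power (2-side alpha = 0.05". With pooled variance and no continuity correction:

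n per arm = [1.960 × √(2 × 0.259 × 0.741) + 0.842 × √(0.304 × 0.696 + 0.214 × 0.786)]² / 0.090² ≈ 371.

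Two arms give 742 evaluable women, and 742/0.95 = 781.1, rounded up to 782. The figure reproduces and matches section 5.1: "We will use a 1:1 randomization scheme targeting 391 pregnant women in each treatment arm". The check below uses 371 evaluable women per arm.

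**Assumptions for anaemia (none is in the documents).** Normally distributed haemoglobin at baseline and three follow-ups; 35% of SP-arm samples below the cut; a treatment effect of 0.19-0.20 SD; baseline/follow-up correlations of 0.3, 0.5 and 0.6, paired with correlations among follow-ups of 0.5, 0.6 and 0.65. Anaemia is analysed as binary by logistic GEE with robust standard errors, with and without continuous baseline.

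| Baseline correlation | 400 runs | 400 runs, repeated | Separate 1,000-run check |
|---|---|---|---|
| 0.3 | 75% → 79% | 78% → 81% | 77% → 81% |
| 0.5 | 78% → 86% | 78% → 86% | 77% → 88% |
| 0.6 | 75% → 88% | 75% → 88% | 74% → 91% |

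Simulation error at 400 runs is √(0.78 × 0.22/400) ≈ 2 points. The 400-run gains are about 3-4, 8 and 13 points. The 1,000-run check came out somewhat higher at 0.5 and 0.6 (11 and 17), so 3 to 13 is not an inflated range.

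The repeated 400-run set corresponded to about 10%, 32% and 53% more information. At correlation 0.5 that implies (1.960 + 0.772) × √1.32 − 1.960 = 1.18, or 88% power from 78%, in line with the larger run.

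With 10% of samples below the cut, an effect of 0.25 SD and correlation 0.5, power rose from 70% to 77% (400 runs) or 79% (1,000 runs).

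**If unadjusted power is higher.** For one continuous follow-up value, adjusted power = Φ[(1.960 + z_base)/√(1 − ρ²) − 1.960]. With 95% base power and ρ = 0.5: (1.960 + 1.645)/√0.75 = 4.163, and Φ(2.203) ≈ 98.6%, a gain of 3.6 points.

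**Role of the enrolment sample.** A sample taken before the first dose cannot show a treatment effect. If it counts as one of four outcome samples, the average difference in prevalence shrinks by a quarter. In the 1,000-run check, unadjusted power then fell from 70-77% to 52-60%.

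**Parasitaemia.** Section 1.2 reports prevalences of 40.5% (3-dose SP) and 5.2% (monthly DP) in the earlier trial. With 371 per arm and one sample each, power is about 100%, so there is nothing to gain. A binary correlation of 0.5 is not attainable there either: with 40.5% positive at baseline and 5.2% at follow-up, the maximum is √[(0.052/0.948)/(0.405/0.595)] = 0.28.

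**The case against.** The strongest reply is that the gain depends on a chosen starting power and that the documents point higher. Section 1.1 reports a significant reduction in maternal anaemia with monthly DP against 3-dose SP. Section 1.2 gives 100 and 106 women randomised to those arms. Scaling a just-significant z of 1.96 from about 103 to 371 per arm gives 1.96 × √(371/103) = 3.72, or about 96% power. Adjustment at ρ = 0.5 then gives 3.72/√0.75 = 4.30, or about 99%, a gain of about 3 points. This stands as a bound on the claim. It does not remove it, because the comparator here is monthly SP, against which the effect may be smaller.

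The simulated schedule is also simplified. A week-20 count in a woman enrolled from week 16 to before about week 18 coincides with her first dose, and women enrolled at about 18 to 20 weeks have no week-20 draw. This too stands as a limit on the figures.

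A reader might infer three stronger things that the documents do not support:

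- That the plan rules out baseline adjustment. It does not; adjustment is optional and unspecified.
- That the unadjusted result is biased by chance imbalance at enrolment. Under randomisation the standard error already covers that, and the unadjusted GEE estimates the marginal contrast directly.
- That parasitaemia loses similar power. The earlier trial's rates contradict this. In addition, Table 3 defines that outcome by microscopy and LAMP, so enrolment qPCR is a related prognostic measure and not the outcome's own baseline.

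**Conclusion.** The point holds for maternal anaemia, as a minor loss of efficiency. A baseline collected in every woman is not pre-specified in the model, and the clause that might admit it is discretionary and aimed at confounding. Under assumed correlations of 0.3 to 0.6 and unadjusted power near 75-78%, the gain forgone is about 3 to 13 points, and about 8 at 0.5. It falls to about 4 points at 0.5 if unadjusted power is near 95%. Prevalence, effect size, correlation and base power are all assumptions, so no single figure is a property of this plan. For parasitaemia the only case is consistency and pre-specification.

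**What to change.** In section 8.1.3:

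1. Always include enrolment haemoglobin, as a continuous covariate, in the maternal anaemia GEE at both cut-offs.
2. Report a standardised prevalence ratio or difference with a matching robust or bootstrap variance. A baseline term in a logistic GEE otherwise turns the odds ratio from marginal to conditional.
3. State that the enrolment sample is baseline and is not among the routine haemoglobin measurements in Table 3.
4. Optionally, handle enrolment parasite status the same way in the parasitaemia GEE, using the smear, or qPCR as a prognostic covariate.

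The cost is a few sentences in the analysis plan and a small standardisation step. No new data, visits or participants are needed.
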